ATTACHMENT 3 HEPATITIS B VIRUS (HBV) SCREENING

Subjects must undergo screening for HBV. At a minimum, this includes testing for HBsAg (HBV surface antigen), anti-HBs (HBV surface antibody), and anti-HBc total (HBV core antibody total):

- Subjects who test negative for all HBV screening tests (ie, HBsAg-, anti-HBc-, and anti-HBs-) are *eligible* for this study.
- Subjects who test **negative** for surface antigen (HBsAg-) and test **positive** for core antibody (anti-HBc+) *and* surface antibody (anti-HBs+) are *eligible* for this study.
- Subjects who test **positive only** for **surface antibody** (anti-HBs+) are *eligible* for this study.
- Subjects who test **positive** for surface antigen (HBsAg+) are NOT eligible for this study, regardless of the results of other hepatitis B tests.
- Subjects who test **positive only** for **core antibody** (anti-HBc+) are *NOT eligible* for this study.

For subjects who are not eligible for this study due to HBV test results, consultation with a physician with expertise in the treatment of hepatitis B virus infection is recommended.

| Eligibility based on hepatitis B virus test results | | | | | | |
|---|---|---|--|--|--|--|
| | Hepatitis B test result | | | | | |
| Action | Hepatitis B surface antigen (HBsAg) | Hepatitis B surface antibody (anti-HBs) | Hepatitis B core antibody (anti-HBc total) | | | |
| | | | | | | |
| Include | _ | _ | | | | |
| | | + | + | | | |
| | | + | | | | |
| | | | | | | |
| Exclude | + | — or + | — or + | | | |
| | | _ | + | | | |

ATTACHMENT 4: ANTICIPATED EVENTS

An anticipated event is an adverse event (serious or non-serious) that commonly occurs as a consequence of the underlying disease or condition under investigation (disease related) or background regimen.

For the purposes of this study, the following events will be considered anticipated events:

• Events related to the progression of the disease under study.

These events will be captured on the CRF and in the database, and will be reported to the Sponsor as described in Section 12.3.1, All Adverse Events. Any event that meets serious adverse event criteria will be reported to the Sponsor within the appropriate timeline as described in Section 12.3.2, Serious Adverse Events. These anticipated events are exempt from expedited reporting as individual single cases to Health Authorities. However, if based on an aggregate review, it is determined that an anticipated event is possibly related to study drug, the Sponsor will report these events in an expedited manner.

Anticipated Event Review Committee (ARC)

An ARC will be established to perform reviews of pre-specified events at an aggregate level. The ARC is a safety committee within the Sponsor's organization that is independent of the Sponsor's study team. The ARC will meet to aid in the recommendation to the Sponsor's study team as to whether there is a reasonable possibility that an anticipated event is related to the study drug.

Statistical Analysis

Details of statistical analysis of anticipated events, including the frequency of review and threshold to trigger an aggregate analysis of anticipated event will be provided in a separate Anticipated Events Safety Monitoring Plan (ASMP).

ATTACHMENT 5: SLIT LAMP EVALUATIONS

Through Week 52, all subjects are required to have slit lamp evaluations performed by an ophthalmologist/optometrist during the study at intervals (based on JIA subtype, ANA test results, age at JIA onset, and JIA duration) as specified in the table below. After Week 52, slit lamp evaluations will be performed at the discretion of the investigator and per standard of care. The date of the screening visit and the ANA test results during screening (as applicable depending on the JIA subtype) should be used to determine when the first slit lamp evaluation should be performed during the study. The interval for the slit lamp evaluations may be adjusted thereafter based on the subject's ANA test results and JIA disease duration after screening. However, once a subject tests positive for ANA at any time during the study (and regardless if the subject subsequently tests negative for ANA), the subject should be considered ANA positive when determining the frequency of slit lamp evaluations.

If a subject develops uveitis during the study, the subject's continued participation in the study is at the discretion of the investigator and Sponsor, and slit lamp evaluations should be performed according to disease course.

Intervals for Slit Lamp Evaluations

| JIA Subtype | ANA | Age at JIA onset (in years) | JIA duration (in years) | Slit Lamp Evaluation Interval (in months) |
|--|-----------------|--------------------------------|----------------------------|--|
| | | - | ≤4 | ≤3 |
| | | ≤6 | >4 and <7 | ≤6 |
| OA extended | Positive (+) | | ≥7 | ≤12 |
| Polyarticular RF-negative | | >6 | ≤2 | ≤6 |
| Juvenile PSA | | -0 | >2 | ≤12 |
| Juvenile I SA | Negative (-) ≤6 | | ≤4 | ≤6 |
| | | | >4 | ≤12 |
| | | >6 | N/A | ≤12 |
| ERA | N/A | N/A | N/A | ≤12 |
| Polyarticular RF-positive Systemic with polyarticular course without systemic symptoms | N/A | N/A | N/A | ≤12 |

ANA = antinuclear antibody; ERA = enthesitis-related arthritis; JIA= juvenile idiopathic arthritis; N/A = not applicable; OA = oligoarticular; PSA = psoriatic arthritis; RF = rheumatoid factor

Adapted from: Heiligenhaus et al, 2007⁸ and Heiligenhaus et at, 2015⁷

ATTACHMENT 6: EXTENDED TREATMENT PERIOD

INTRODUCTION

As indicated in Section 3.1.4, subjects who have completed the full trial period of 252 weeks and for whom drug is proven beneficial but is not commercially available for the pJIA indication (or subject does not qualify for insurance to pay for the drug), will continue to be provided with IV golimumab by the Sponsor. This attachment outlines the procedures and assessments that should be followed, for provision of golimumab to eligible subjects after completion of the main study, in the ETP.

Eligible subjects are <18 years of age at the time of their Week 252 visit of the main study, have received the Week 244 infusion, and completed the Week 252 assessments. The investigator must confirm that the subject, in their opinion, will benefit from continued golimumab treatment, and it is not commercially available for the pJIA indication (or subject does not qualify for insurance to pay for the drug). The ETP begins at Week 252 of the main study and will continue until the subject either turns 18 years of age, is no longer benefiting from golimumab treatment, or marketing authorization is obtained for golimumab in the treatment of pJIA in the subject's respective country and subject qualifies for insurance to pay for the drug. Subjects may decide to stop golimumab treatment (withdraw consent) at any time.

Subjects will receive the same golimumab treatment (80 mg/m² every 8 weeks administered intravenously; maximum dose 240 mg) that they received prior to Week 252 in the main study.

Subject visits and monitoring (eg, laboratory evaluation, TB evaluation) should occur at the investigator's discretion and as per usual clinical practice for a subject with pJIA receiving a TNF α inhibitor. Physicians participating in this ETP must agree to take full responsibility for the use of this product.

Local regulations and guidelines related to participation in the ETP, including but not limited to period approvals, and re-approvals are the responsibility of the physician.

The physician must ensure that any local requirements for safety reporting to Health Authorities and/or Independent Ethics Committees/Institutional Review Boards, if appropriate, are met.

During the ETP, concomitant medications including those for pJIA will be administered at the discretion of the investigator for all subjects. During the course of the ETP, in situations where a departure from the protocol or standard of care is unavoidable, the investigator or other physician in attendance will contact the appropriate Sponsor (see Contact Information page[s] provided separately). Except in emergency situations, this contact should be made before implementing any departure from the protocol or standard of care. In all cases, contact with the Sponsor must be made as soon as possible to discuss the situation and agree on an appropriate course of action. The data recorded in the subject's medical records should reflect any departure from the protocol/standard of care.

ELIGIBILITY CRITERIA

The investigator must confirm and document in subject's medical records the necessity of continuing golimumab treatment in the ETP and that switching to another commercially available treatment is not in the best interest of the subject. Additionally, for subjects to be eligible for the ETP, the investigator must document that golimumab is not commercially available for the pJIA indication (and subject does not qualify for insurance to pay for the drug). Documentation should be done at the following timepoints:

- At Week 252, after the subject has completed participation in the study (ie, the Week 252 assessments have been completed)
- At each subsequent year the subject participates in the ETP (via attestation form).

Each subject must continue to satisfy specified inclusion and exclusion criteria as well as prohibitions and restrictions as noted in Sections 4.1, 4.2, and 4.3, respectively. For questions related to eligibility, the investigator should contact the Sponsor for clarification.

In addition, specific criteria for the ETP are noted below.

Inclusion Criteria

Each potential subject must satisfy the following criteria to continue to receive golimumab as part of the ETP. Criteria from Section 4.1 that apply are referenced below.

- 1. Subjects must be less than 18 years of age.
- 2. Subject has received the Week 244 infusion and completed the Week 252 assessments as outlined in Table 3 of the Time and Events Schedule of the Protocol.
- 3. Each subject (or their legally acceptable representative) must sign an ICF indicating that he or she understands the purpose of and the procedures required for the ETP. Assent is also required of children capable of understanding the nature of the study (typically 7 years of age and older and per local regulations) as described in Section 16.2.3, Informed Consent.
- 4. Subjects must continue to have pJIA as specified in inclusion criterion #3 in Section 4.1. Subjects may remain in treatment if in remission, but if the diagnosis is thought to change from pJIA, treatment should be discontinued.
- 5. Subjects must continue to meet eligibility criteria for TB (Inclusion criterion #10 in Section 4.1)
- 6. Subjects must continue to avoid pregnancy (Inclusion criteria #12, #13, and #14 in Section 4.1).

Exclusion Criteria

The specific exclusion criteria listed in Section 4.2 that apply are noted below with the numbers referring to that section. If a subject meets these criteria, he/she will be excluded from continued participation in the ETP.

- 1. Pregnancy (in a female) or plans for pregnancy (in females or males) are exclusionary (Exclusion criteria #41 and #42 in Section 4.2).
- 2. Subjects with a BSA >3.0 m² (Exclusion criterion #46 in Section 4.2).

Prohibitions and Restrictions

All subjects must continue to comply with all the prohibitions and restrictions as noted in Section 4.3, with the exception of the prohibition regarding intramuscular corticosteroids. Contrary to the main study, subjects may receive intramuscular administration of corticosteroids for the treatment of pJIA as deemed necessary by the investigator in the ETP. However, these occurrences should be limited. If needed for ongoing control of pJIA, thought should be given to the need to change to a different medication and the subject stopping participation in the ETP.

PROCEDURES AND ACTIVITIES

Subjects who enter the ETP at the Week 252 visit will continue to receive 80 mg/m² golimumab (maximum dose 240 mg) administered as IV infusions over 30±10 minutes q8w (±1 week) until discontinuation of golimumab treatment, as described below.

The following procedures and activities must be performed by the investigator during the ETP:

- Completion of the attestation form to document that a subject is benefiting from treatment annually.
- Record AEs considered to be related to golimumab, all SAEs (regardless of causality to golimumab), pregnancy, and events of special interest (ie, malignancy and TB) on the CRF. Refer to Section 12.3.1 for procedures for reporting these events.
- Record concomitant medications associated with or used to treat AEs and SAEs on the CRF.

Subject visits and monitoring (eg, laboratory evaluation, TB evaluation) should occur at the investigator's discretion and as per usual clinical practice for a subject with pJIA receiving a $TNF\alpha$ inhibitor. Physicians participating in this ETP must agree to take full responsibility for the use of this product.

GOLIMUMAB STORAGE, PREPARATION, DOSAGE, ADMINISTRATION, and ACCOUNTABILITY

Golimumab will be supplied by the Sponsor during the ETP. The first dose of golimumab in the ETP will be administered at Week 252 after completion of the Week 252 assessments. Subjects will receive 80 mg/m² golimumab (maximum dose 240 mg) IV infusions q8w. The q8w

(± 1 week) dosing regimen should be adhered to and infusions may only be missed for safety reasons. Exceptions to the q8w (± 1 week) dosing regimen should only be made if infusions are off-schedule for safety reasons. In these instances, the minimum time between infusions can be 4 weeks to enable the subject to resume the q8w dosing regimen.

Refer to Sections 14.1, 14.2, and 14.3 for details about the physical description, packaging, and labeling of golimumab, respectively.

Investigators will be responsible for ensuring that golimumab is stored according to the specifications outlined in Section 14.4.

Investigators/site personnel will also be responsible for scheduling golimumab infusions and ensuring correct administration.

Prior to preparing a dose for infusion, the subject's current weight and height should be used to obtain the subject's body surface area (BSA). The subject's BSA will be calculated prior to each infusion using the Mosteller equation and the dose of golimumab adjusted as needed to maintain the dose at 80 mg/m². A maximum dose of 240 mg cannot be exceeded in any circumstance, even if a subject's BSA is large enough to yield a higher calculated dose.

The golimumab infusions should be prepared and administered by a healthcare professional as noted in the Golimumab Preparation and Administration Instructions.

The investigator is responsible for ensuring that all golimumab received at the site is inventoried and accounted for throughout the ETP. All study drug should be stored and disposed of according to the Sponsor's instructions. Site personnel must not combine contents of the study drug containers.

Golimumab should be handled in strict accordance with the Golimumab Preparation and Administration Instructions and the container label and should be stored in a limited-access area or in a locked cabinet under appropriate environmental conditions. When the site is an authorized destruction unit and study drug supplies are destroyed on-site, this must also be documented on the drug return form.

Potentially hazardous materials such as used ampules, needles, syringes and vials containing hazardous liquids, should be disposed of immediately in a safe manner and therefore will not be retained for drug accountability purposes.

Golimumab should be dispensed under the supervision of the investigator or a qualified member of the site personnel, or by a hospital/clinic pharmacist. Golimumab will be supplied only to subjects participating in the ETP. Golimumab returned to the site/IWRS stock must not be dispensed again, even to the same subject. Golimumab may not be relabeled or reassigned for use by other subjects.

CONCOMITANT MEDICATIONS

Concomitant medications including medications for pJIA may be administered and adjusted at the discretion of the investigator but should not violate any prohibitions and restrictions noted in Section 4.3, Prohibitions and Restrictions, with the exception noted in Section 4.3 concerning IM corticosteroids.

Concomitant medications associated with, or used to treat, AEs and SAEs should be recorded in the CRF.

Methotrexate will not be supplied by the Sponsor.

DISCONTINUATION OF GOLIMUMAB/TREATMENT WITHDRAWAL CRITERIA

The subjects may at any time withdraw consent and discontinue treatment with golimumab. If a subject's golimumab treatment is discontinued, this will result in automatic permanent withdrawal of the subject from the ETP. A subject's golimumab treatment provided via this ETP will be permanently discontinued when any of the following occur:

- The subject is no longer benefiting from golimumab treatment.
- The subject turns 18 years of age.
- Golimumab becomes commercially available in the subject's respective country and the subject's insurance will pay for the drug.

A subject's golimumab treatment should also be permanently discontinued if any of the criteria in Section 10.2. Discontinuation of Study Treatment, are met.

When a subject discontinues study treatment, a follow-up evaluation should occur approximately 8 weeks after the last infusion of study agent to ensure that there are no safety concerns.

ADVERSE EVENT REPORTING

AEs considered by the investigator to be related to study drug (as defined in Section 12.3.1), SAEs (as defined in Section 12.1.1), pregnancy, and events of special interest (ie, malignancy and TB) are required to be reported in the ETP on the CRF. Refer to the following sections for procedures for reporting these events: Section 12.3.1 for AEs, Section 12.3.2 for SAEs, Section 12.3.3 for pregnancy, and Section 12.4 for events of special interest.

PRODUCT QUALITY COMPLAINTS

Refer to Section 13 for definition of PQCs during the ETP. If a defect is combined with an SAE during the ETP, the study site personnel must report the PQC to the Sponsor according to the timelines and procedures for an SAE.

The names (and corresponding telephone numbers) of the individuals who should be contacted regarding product quality issues are listed on the Contact Information page(s), which will be provided as a separate document.

ETHICAL ASPECTS

Refer to Section 16 for details regarding ethical aspects of the ETP.

Extended Treatment Period Considerations

Potential subjects will be fully informed of the risks and requirements of the ETP and, during the ETP, subjects will be given any new information that may affect their decision to continue participation. They will be told that their consent to participate in the ETP is voluntary and may be withdrawn at any time with no reason given and without penalty or loss of benefits to which they would otherwise be entitled. Only subjects who are fully able to understand the risks, benefits, and potential adverse events of the ETP, and provide their consent voluntarily will be enrolled. For additional details regarding the ICF process, see Section 16.1.

ADMINISTRATIVE REQUIREMENTS

Protocol Amendments

If a modification to ETP is needed, a formal protocol amendment will be issued by the Sponsor. Refer to Section 17.1 for additional details about the procedures that will be followed for the implementation of a protocol amendment.

Documentation Required for Extended Treatment Period

At a minimum, the type and level of detail of subject's medical records available for a subject participating in the ETP should be consistent with that commonly recorded at the site as a basis for standard medical care. Subject records must be available for review of AEs considered to be related to study drug and SAEs. The author of an entry in the subject's medical records should be identifiable

Record Retention

Refer to Section 17.7 for details regarding record retention during the ETP.

Monitoring

The Sponsor will perform on-site monitoring visits as necessary. The monitor will record dates of the visits in a site visit log that will be kept at the site. The nature and location of all subject's medical records will be identified to ensure that all sources of original data are known to the Sponsor and site personnel and are accessible for verification by the Sponsor site contact. If electronic records are maintained at the site, the method of verification must be discussed with the site personnel.

Direct access to subject's medical records must be allowed for the purpose of verification of the data reported to the Sponsor. Findings from this review of the subject's medical records will be discussed with the site personnel. The Sponsor expects that, during monitoring visits, the relevant site personnel will be available, the subject's medical records will be accessible, and a suitable environment will be provided for review of ETP-related documents. The monitor will

meet with the investigator as needed during the ETP to provide feedback on the administration of the ETP.

Extended Treatment Period Completion/Termination

Extended Treatment Period Completion

The ETP is considered completed when the youngest subject enrolled in the ETP is 18 years of age or the last subject participating in the ETP discontinues.

Extended Treatment Period Termination

The Sponsor reserves the right to close the study site or terminate the ETP at any time for any reason at the sole discretion of the Sponsor. Study sites will be closed by the Sponsor upon ETP completion. Refer to Section 17.9.2 for further details regarding site closure and reasons for early closure of a site by the Sponsor.

Use of Information and Publication

Refer to Section 17.11 for details regarding the use of information and publication of data generated as a result of this ETP.

INVESTIGATOR AGREEMENT

SIMPONI® (golimumab) for Intravenous Use

Clinical Protocol CNTO148JIA3003 Amendment INT-4

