3.1.3. Week 52 Through Week 252 (Long-term Extension)

Subjects who complete the study at Week 52 will have the option to enter into the LTE phase of this study. Subjects who opt not to enter the LTE will be encouraged to complete an additional 8-week safety follow-up visit following the last administration of study agent.

During the LTE, all subjects will continue to receive golimumab q8w (±1 week) through Week 244. For subjects who have completed the trial period of 252 weeks and for whom drug is proven beneficial but is not commercially available for pJIA indication (or patient does not qualify for insurance to pay for the drug) IV golimumab will continue to be provided by the Sponsor, as described in Section 3.1.4. Between Week 52 and Week 252, disease activity will be

monitored and assessed by investigators, and benefit of treatment will be documented in the subject's source documents by investigators on a yearly basis via an attestation form; infusions and safety measurements will be done at the investigative site according to the Time and Events Schedule.

As noted above, after Week 28, subjects will be permitted to change/add MTX, other DMARDs, corticosteroids, and NSAIDs, including increases or decreases in BSA-based dosing (where appropriate) for these classes of agents as outlined in Section 8.

All subjects who complete the Week 244 visit are expected to participate in the safety follow-up visit at Week 252. Those subjects who discontinue study agent at any time before Week 244 are also expected to return for a safety follow-up visit approximately 8 weeks after the last administration of study agent.

A database lock will occur at Week 252.

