4. SUBJECT POPULATION

Screening for eligible subjects will be performed within 6 weeks before administration of the study drug.

The inclusion and exclusion criteria for enrolling subjects in this study are described in the following 2 subsections. If there is a question about the inclusion or exclusion criteria below, the investigator should consult with the appropriate Sponsor representative before enrolling a subject in the study.

For a discussion of the statistical considerations of subject selection, refer to Section 11.2, Sample Size Determination.

Deviations from the inclusion and exclusion criteria are not allowed because they can potentially jeopardize the scientific integrity of the study, regulatory acceptability, or subject safety. Therefore, adherence to the criteria as specified in the protocol is essential.

Approximately 120 subjects will be enrolled in this study. Enrolled subjects who discontinue study treatment or withdraw from study participation will not be replaced with new subjects.

Retesting of an abnormal screening value that leads to exclusion is allowed only once using an unscheduled visit during the screening period to reassess eligibility. This should be considered only if there is no anticipated impact on subject safety.

Eligibility criteria for the ETP are provided in Attachment 6. Prohibitions and restrictions during the ETP are also provided in Attachment 6.

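### The Attachment 6 eligibility test for the Extended Treatment Period says *and* where Section 3.1.3 and the Attachment 6 Introduction say *or*, so a benefiting child whose country markets golimumab for pJIA but whose insurance does not pay could be refused promised drug

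*Protocol*

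**What the plan says.** Protocol Section 4 tells the investigator where to look: "Eligibility criteria for the ETP are provided in Attachment 6".

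Under the Eligibility Criteria heading of that attachment, the investigator has to put this condition on record: "golimumab is not commercially available for the pJIA indication (and subject does not qualify for insurance to pay for the drug"). This is done at Week 252 and again later: "At each subsequent year the subject participates in the ETP (via attestation form"). The same paragraph requires a record that a switch to a different marketed treatment would not serve the child, and the section directs eligibility questions to the Sponsor.

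Other places state the access rule differently.

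- **Section 3.1.3:** drug is supplied to those who benefit if it is not commercially available for pJIA, "or patient does not qualify for insurance to pay for the drug) IV golimumab will continue to be provided by the Sponsor", with a reference to Section 3.1.4.
- **Attachment 6 Introduction, supply statement:** opens "As indicated in Section 3.1.4, subjects who have completed the full trial period of 252 weeks" and ends with the alternative "or subject does not qualify for insurance to pay for the drug), will continue to be provided with IV golimumab by the Sponsor".
- **Attachment 6 Introduction, what the investigator must confirm:** "it is not commercially available for the pJIA indication (or subject does not qualify for insurance to pay for the drug").
- **Section 3.1.4 and the Synopsis:** lack of commercial availability for pJIA only, with no mention of insurance.
- **Attachment 6 Introduction, stop rule:** treatment runs until, among other reasons, "marketing authorization is obtained for golimumab in the treatment of pJIA in the subject's respective country and subject qualifies for insurance" to pay.
- **Attachment 6 Discontinuation criteria:** stop when golimumab becomes commercially available in the child's country and the child's insurance will pay. No indication is named.

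**The concern.** One attachment gives the investigator two mandatory tests that cannot both be the rule: confirm A *or* B in the Introduction, document A *and* B in the Eligibility Criteria. The stricter wording sits under the heading to which Section 4 points and is tied to required documentation, so a careful investigator or monitor could well apply it.

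Continuity of treatment is at stake. The first ETP dose is due at Week 252, so a child who is refused has the last study infusion at Week 244, although two parts of the protocol say the Sponsor will go on supplying the drug. The analyses are not at stake: the Week 28 and Week 52 pharmacokinetic, efficacy and safety results all precede the ETP.

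**Working it through.** The protocol gives no figure to reproduce. The check is a comparison of rules for a child who benefits, is under 18 at Week 252 and meets the other ETP criteria.

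**Notation.** M = golimumab is on sale for pJIA in the child's country. I = the child's insurance pays for it.

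**Rules.**
- Section 3.1.3 and Attachment 6 Introduction: supply if (not M) or (not I).
- Attachment 6 Eligibility Criteria: supply if (not M) and (not I).
- Section 3.1.4 and Synopsis: supply if (not M).
- Stop rule, taking availability to mean availability for pJIA: stop if M and I.

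| Case | 3.1.3 and Introduction | Eligibility Criteria | 3.1.4 and Synopsis | Stop rule |
|---|---|---|---|---|
| Not on sale, not insured | in | in | in | continue |
| On sale, not insured | in | **out** | **out** | continue |
| Not on sale, insured | in | **out** | in | continue |
| On sale, insured | out | out | out | stop |

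**Reading the table.**
1. Since not (M and I) equals (not M) or (not I), the stop rule is the exact complement of the *or* entry rule. It is not the complement of the *and* rule. This points to *or* as the intended rule.
2. The second row is the case with a plausible loss of treatment. The Eligibility Criteria, Section 3.1.4 and the Synopsis all give no entry; Section 3.1.3 and the Introduction promise drug.
3. The third row is also a textual conflict, but a doubtful one. The documents describe no route by which insurance pays for a drug not on sale for the indication, and if insurance did pay the child would have other access. It shows no loss of treatment.
4. Section 3.1.3 defers to Section 3.1.4, and the Introduction attributes its rule to Section 3.1.4, yet Section 3.1.4 has no insurance alternative. Correcting the Eligibility Criteria alone would leave that gap.

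**The two stop rules.** The complement in step 1 depends on adding the pJIA indication to the Discontinuation criteria, which do not name it. Section 3.2.3 says intravenous golimumab is approved for adult rheumatoid arthritis. Read literally, the Discontinuation criteria would stop an insured child in a country that sells the drug for that use only. The Introduction's stop rule names pJIA but turns on marketing authorization rather than commercial availability, so it could stop an insured child where the drug is authorised but not yet on sale.

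**Children already in the ETP.** The Eligibility Criteria repeat the documentation yearly. The Discontinuation criteria, and Section 10.2 to which they refer, list no matching reason to stop, and the ETP procedures describe the yearly attestation as a record of benefit.

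**Size.**
- Age limit: 252 weeks is 252 × 7 / 365.25 = 4.83 years, so a child must be younger than about 18 − 4.83 = 13.2 years at Week 0. Section 3.1 expects about 10% aged 2 to under 6 and 20% aged 6 to under 12, which is 0.30 × 120 = 36 children before dropout, plus an unknown part of the 70% aged 12 to under 18.
- How many of these would be in the on-sale, not-insured case cannot be derived.
- Per refused child with no other access: 365.25 / 56 = 6.5 infusions a year, until age 18, loss of benefit or another stop.

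**The case against.** The strongest reply is that this is a drafting slip in an access clause after the trial proper, with a remedy built in. The Introduction tells the same investigator to confirm the *or* condition, and the section containing the *and* sends eligibility questions to the Sponsor. That stands in part. A reader might infer that the child in question is certain to be refused; the documents support only that refusal could happen. The contact line still does not remove the contradiction, because an investigator who reads a clear *and* may see no question to ask.

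Second, the Eligibility Criteria are not the only cause. Section 3.1.4 and the Synopsis also leave the child out, and the stated reasons for Amendment 4 mention availability alone. This stands. It widens the repair and leaves the choice of rule with the Sponsor, although Section 3.1.3, the Introduction and the paired conditions in both stop rules favour *or*.

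Third, the affected group is narrow: under 18 at Week 252, still benefiting, with a switch not in the child's interest, in a country that markets the drug for pJIA, and without cover. This also stands; the group may be empty.

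A reader might also infer that a child already in the ETP must be stopped at the yearly documentation. The text does not go that far. It is contradictory on this point, but no discontinuation criterion requires the stop.

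**Conclusion.** The Attachment 6 Eligibility Criteria are wrong as written, and the point is minor. They conflict with Section 3.1.3 and with two statements in their own attachment, while Section 3.1.4 and the Synopsis state a third rule. One combination carries a plausible loss of treatment: drug on sale for pJIA, insurance not paying. An investigator following the Eligibility Criteria could refuse such a child drug that the protocol elsewhere promises.

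The conflict of wording is certain. The refusal is possible only, and the number of children cannot be derived and may be small or zero. Counting logical cases should not be taken as a measure of harm, since the cases are unweighted and one of them is doubtful. The conclusion that *or* is intended rests on reading the Discontinuation criteria as referring to pJIA, which they do not say, and on giving Section 3.1.3 and the Introduction more weight than Section 3.1.4 and the Synopsis.

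**What to change.** 1. In the Attachment 6 Eligibility Criteria, change *and* to *or* before the insurance condition, so that it governs both the Week 252 and the yearly documentation.
2. Add the same *or* insurance alternative to Section 3.1.4 and to the Synopsis.
3. Use one stop rule in the Attachment 6 Introduction and the Discontinuation criteria: golimumab is commercially available for the pJIA indication in the child's country, and the child's insurance will pay. The Introduction then drops marketing authorization as the trigger, and the Discontinuation criteria gain the indication.

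Entry, yearly documentation and both stop rules then agree in all four cases of the table. The cost is five short wording edits in one amendment. The downside is that the Sponsor may supply a few more children, whom Section 3.1.3 and the Introduction already promise to supply. If the Sponsor intends a narrower rule, it should say so and withdraw the promise in those two places.
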